Review menarche status with date of menarche, if applicable	X	X	X	X	X		X		X	X		For participants <18 years of age. If the participant reaches menarche at any time during the trial and is sexually active, pregnancy testing and contraception requirements will apply. See Section 10.4, Appendix 4.	
Concomitant medications	X	X	X	X	X	X	X	X	X	X	X		
AEs	X	X	X	X	X	X	X	X	X	X	X	Any events that occur after signing the ICF or assent are considered AEs as defined in Section 10.3, Appendix 3. For AESIs, additional data could be collected (Section 8.3.3).	
Physical Evaluation													
Height	X								X				
Weight	X	X					X		X	X			

	Period I	Period II									Period III	Comments	
	Screening	Baseline	Treatment Period									Post-treatment Follow-Up	
Visit Number	1	2	3	4	5	6	7	8	9	ED	801		
Week Relative to Study Drug Start	≤30 (days)	0	2	4	8	12	16	20	24	—	12 weeks post last dose		
Visit Interval Tolerance (Days)		—	±3	±3	±5	±5	±5	±5	±5	—	±7		
Visit Detail						T		T					
Vital signs	X	X					X		X	X		Includes pulse rate, blood pressure, respiratory rate, and temperature. Measured after participant has been sitting at least 5 minutes. Use size appropriate blood pressure cuff.	
Physical examination	X								X	X		The physical examination is performed (excludes pelvic and rectal, unless clinically indicated). Full skin examination is required for BSA calculation.	
Symptom-directed physical assessment		X	X	X	X		X				X	As indicated based on participant status and standard of care. May be performed by qualified personnel per local regulations.	
Participant Diary (Electronic)													
Diary dispensed	X											Diary includes daily collection of Pruritus NRS, Sleep-Loss Scale, and Skin Pain NRS; weekly collection of POEM; bi-weekly collection of study drug administration information (as applicable). TCS usage will be collected daily beginning at V2. Pruritus NRS and Sleep-Loss Scale should be completed a minimum of 4 of 7 days before baseline.	
Review diary for completion of PRO and TCS assessments		X	X	X	X	X	X	X	X	X		For details of these assessments, see Section 8.1.	
Drug administration diary compliance check					X	X	X	X	X	X			
Diary return									X	X			

	Period I	Period II									Period III	Comments	
	Screening	Baseline	Treatment Period									Post-treatment Follow-Up	
Visit Number	1	2	3	4	5	6	7	8	9	ED	801		
Week Relative to Study Drug Start	≤30 (days)	0	2	4	8	12	16	20	24	—	12 weeks post last dose		

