### 6.8.1. Permitted Treatments and Procedures

The following therapies will **be permitted** during the study:

Permitted Concomitant Medications and Vaccines	Comments
Medications	
Medications for medical conditions other than AD, e.g., hypertension and diabetes	
Low and/or mid-potency TCS, TCIs (e.g., tacrolimus and pimecrolimus), or topical PDE-4	Permitted as needed on AD lesions and must be documented in the diary.

Permitted Concomitant Medications and Vaccines	Comments
inhibitors (e.g., crisaborole) for treatment of AD	
High-potency TCS for treatment of AD	Permitted up to 10 days
Non-medicated moisturizers	
Intranasal corticosteroids	
Inhaled corticosteroids and bronchodilators to control asthma	
Single intra-articular (bursa, tendons, and ligaments) corticosteroid injection	
Non-sedating antihistamines	
Ophthalmic drugs containing antihistamines, corticosteroids, or other immunosuppressants	
Allergen immunotherapies	If on maintenance dose.
Leukotriene inhibitors	
Systemic and topical anti-infectives	For treatment of acute infections.
Sedating systemic antihistamines including, but not limited to, alimemazine, chlorphenamine, clemastine, cyproheptadine, diphenhydramine, hydroxyzine, ketotifen, and promethazine	On an as-needed basis.
Systemic or oral sleep aid medications	On an as-needed basis.
Recreational use of cannabis and cannabinoid	Not allowed for the treatment of pruritus, pain and/or AD
Vaccines	
Non-live vaccinations	Including non-live SARS-CoV-2 vaccines, RNA vaccines, vaccines with inactive viral elements, and/or non-replicating viral vectors that are clinically indicated.

Abbreviations: AD = atopic dermatitis; PDE-4 = phosphodiesterase-4; RNA = Ribonucleic acid; SARS-CoV-2 = severe acute respiratory syndrome coronavirus 2; TCI = topical calcineurin inhibitors; TCS = topical corticosteroids.

NOTE: in the context of this table, “during the study” = from screening to post-treatment safety follow-up visit.

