### 6.8.4. Topical Treatment for Atopic Dermatitis

The goal of this Phase 3b study is to demonstrate the safety and efficacy of lebrikizumab for moderate-to-severe AD in participants with skin of color. Regular use of non-medicated, non-prescription moisturizers should be used by all participants. During this study, topical therapies may be needed if the participant experiences intolerable clinical worsening of symptoms. If needed, investigators are encouraged to recommend therapy in a staged fashion, beginning with a topical low-potency treatment first, then topical mid-potency treatment if needed. In sensitive skin areas, i.e., face, neck, intertriginous, and genital areas, only low-potency topical treatments should be used.

If AD lesions recur or a participant experiences a flare, as needed use of low- and/or mid-potency TCS, TCI (tacrolimus or pimecrolimus), and/or topical PDE4 inhibitors (crisaborole) may be initiated at the participant’s discretion but must be communicated to the investigator and documented in the patient diary or as concomitant medications. . Escalation to high-potency topical corticosteroid medications should only occur if participants do not respond adequately after at least 7 days of low- or mid-potency TCS, TCI, and/or topical PDE4 inhibitors.(Section 6.8.5). Use of high-potency TCS for more than 10 days is considered rescue

therapy. Participants that receive Rescue Therapy must be discontinued from the study (see Section 7.1). All topical prescription therapy usage must be recorded in the CRF or diary.

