Appendix 1. Definition of Rescue Medications

The AD rescue therapy in this study is defined as: high-potency TCS >10 days, topical JAK inhibitors, and systemic AD therapy. The topical and systemic treatments are defined as follows:

1. Topical AD Treatment (including TCSs, TCI, crisaborole, and Ruxolitinib)

Route of topical treatments includes: Topical and Transdermal.

TCS: ATC code is D07

High Potency TCS: ATC codes are D07AC or D07AD

Low or moderate potency TCS: ATC code is D07, excluding D07AC or D07AD

TCI: PT includes: TACROLIMUS, PIMECROLIMUS

Crisaborole: PT includes: CRISABOROLE

Topical Ruxolitinib: ATC code is D11AH09

2. Systemic AD Treatment (including systemic corticosteroids, immunosuppressant, biologics, and phototherapy/PUVA)

Route of systemic treatments administration includes: Oral, Intra-Arterial, Intramuscular, Intraperitoneal, Intravenous, Subcutaneous, and Transdermal. (This condition applies to the following categories except for phototherapies.)

Systemic Corticosteroids: ATC code is H02

Immunosuppressant: Defined as: ATC2 is L04 or PTs of Abrocitinib or Ruxolitinib excluding PTs mentioned in Biologics

Biologics: Defined as following PTs:

Infliximab, Infliximabum, Etanercept, Etanerceptum, Adalimumab, Adalimumabum, Certolizumab, Certolizumabum, Certolizumab pegol, Golimumab, Golimumabum, Ozoralizumab, Afelimomab, Afelimomabum, Tumor Necrosis Factor Alpha (TNF-) Inhibitors, Tabalumab, Tregalizumab, Anakinra, Basiliximab, Basiliximabum, Daclizumab, Daclizumabum, Tocilizumab, Tocilizumabum, Mepolizumab, Mepolizumabum, Rilonacept, Rilonaceptum, Ustekinumab, Canakinumab, Briakinumab, Fezakinumab, Sirukumab, Sarilumab, Lebrikizumab, Secukinumab, Olokizumab, Gevokizumab, Brodalumab, Ladarixin, Ixekizumab, Dupilumab, Tildrakizumab, Tildrakizumabum, Reslizumab, Reslizumabum, Guselkumab, Guselkumabum, Olamkicept, Fletikumab, Bimekizumab, Mirikizumab, Risankizumab, Abatacept, Ligelizumab, Vedolizumab, Belimumab, Nemolizumab, Tralokinumab, Omalizumab

Phototherapy or PUVA:

Programming search of medication name (actual term or PT) contains 'photo' then medicals to manually review to confirm whether the medication in question is indeed 'Phototherapy' or 'Photochemotherapy'.

PPD

PPD

23 Jun 2023 14:52:57 UTC (Z)

REASON: I approve this document

d5b66f2f-11e1-4ad9-8ea4-c216ad4f48c5

PPD

PPD

12 Jun 2023 15:29:11 UTC (Z)

REASON: I approve this document

7543fdb-1287-4fef-83c0-81a70287c57a

PPD

PPD

09 Jun 2023 20:08:20 UTC (Z)

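### The rules in SAP Appendix 1 can miss or misclassify rescue treatment in the descriptive rescue summaries of SAP 5.10 (minor)

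*SAP*

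**What the plan says.** SAP Appendix 1 opens with the rule: "The AD rescue therapy in this study is defined as: high-potency TCS >10 days, topical JAK inhibitors, and systemic AD therapy". It then says how each part is recognised.

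- **Phototherapy and PUVA** sit in the systemic group, described as "including systemic corticosteroids, immunosuppressant, biologics, and phototherapy/PUVA". They are found by "Programming search of medication name (actual term or PT) contains" the string `photo`. The hits then go to medical staff "to manually review to confirm whether the medication in question is indeed" phototherapy or photochemotherapy.
- **Topical and systemic routes.** Topical routes are Topical and Transdermal. The systemic route list also includes Transdermal. Topical ruxolitinib has its own ATC code (D11AH09), while the systemic immunosuppressant rule takes any ruxolitinib preferred term.
- **High-potency TCS:** "High Potency TCS: ATC codes are D07AC or D07AD". Nothing is said about how days are counted or from which data.

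SAP 5.10 points to Appendix 1 for the definition. It presents rescue use for Weeks 0-16 and Weeks 16-24, with topical and systemic therapy as separate groups. It describes ATC-coded medications with start and stop dates and does not mention the diary.

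In the protocol, 6.8.1 permits high-potency TCS for up to 10 days, and 6.8.4 and 6.8.5 treat longer use as rescue. On recording, 6.8.4 says "All topical prescription therapy usage must be recorded in the CRF or diary", whereas 6.8.5 requires all rescue medication on the CRF. The Schedule of Activities states for the diary that "TCS usage will be collected daily beginning at V2". Section 6.8.2 names PUVA among prohibited therapies, and its abbreviation list expands PUVA as photochemotherapy.

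**The concern.** Followed literally, three of these rules may not return what their headings promise. The phototherapy search does not contain the word PUVA, although PUVA is half of the category it is meant to find, and review of the hits cannot recover a record that was never a hit. One topical ruxolitinib record can satisfy both the topical and the systemic definition, although SAP 5.10 reports the two separately. A threshold expressed in days is paired with an identification rule that contains no days, and the protocol allows the relevant use to be written down in a place the SAP does not name.

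At stake is the accuracy of the rescue tables. In an open-label, single-arm study these tables show the reader how much other AD treatment accompanied the response rates.

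**Working it through.** No figure in the plan depends on these rules, so the check consists of applying each rule as written.

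**1. The string search.** Input: the search term in Appendix 1. PUVA and the two phototherapy words come from the documents; the last three entries are assumed site wordings.

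| Entry | Hit, ignoring case | Hit, case-sensitive (lower-case term) |
|---|---|---|
| Phototherapy | yes | no |
| Photochemotherapy | yes | no |
| PUVA | no | no |
| UVB | no | no |
| narrowband UVB | no | no |
| light therapy | no | no |

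The SAP does not state how case is handled. The rule looks at the reported term or the preferred term, so PUVA is still found if its preferred term contains `photo`. The documents do not show how it would be coded.

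**2. The overlap.** Take a topical ruxolitinib record with ATC code D11AH09 and route Transdermal.

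- Topical rule: the route is listed and the code matches, so it counts as topical.
- Systemic immunosuppressant rule: the preferred term is ruxolitinib and the route is listed, so it also counts as systemic.

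With route Topical, only the first rule applies. Any topical JAK inhibitor use is rescue either way, so the overlap changes the systemic row and not the number of participants with any rescue.

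**3. The day threshold.** Recording duties for high-potency TCS, in order of use:

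- Up to 10 days it is permitted (6.8.1), and 6.8.4 accepts either the CRF or the diary.
- Beyond 10 days it is rescue, and 6.8.5 requires the CRF.

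The CRF-only duty therefore starts when someone has counted past 10. If all use stayed in the diary, there may be no coded record for Appendix 1 to match. If there is a CRF record, the SAP does not say whether days are cumulative, consecutive or taken from dates. As an assumed illustration, as-needed use recorded from Day 20 to Day 80 but applied on 6 days is 80 - 20 + 1 = 61 days by dates and 6 by application. The SAP prescribes neither count.

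**4. Where the flag goes.** SAP 5.2.1 defines the primary population by remaining on treatment to Week 16. Table KGBP.5.3 and SAP 5.4.1 analyse it as observed. The supportive estimands use permanent treatment discontinuation, split by reason. None of these refers to Appendix 1; SAP 5.10 does. The Week 16 rate is responders divided by participants observed on treatment, and neither count contains the flag. Correcting Appendix 1 changes that rate by 0.

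**The case against.** The strongest reply is that the protocol already closes most of the gap. Section 6.8.5 puts all rescue on the CRF. Section 6.8 requires every medication received to be recorded with its dates. Concomitant medications are collected at every visit, and diary TCS entries are reviewed from Visit 2 to Visit 9. A PUVA entry may well be coded to a preferred term containing `photo`. Silence about the diary does not exclude it, and double-classing ruxolitinib changes only one table row.

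Much of this stands. It would be wrong to infer that the protocol allows rescue to be recorded in the diary alone. The diary instruction in 6.8.1, "Permitted as needed on AD lesions and must be documented in the diary", covers low- and mid-potency TCS, calcineurin inhibitors and PDE-4 inhibitors, which are permitted treatments and not rescue. It would also be wrong to infer that the SAP counts high-potency TCS by start and stop dates and so labels intermittent use as rescue, because it states no counting rule.

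The reply does not fully dispose of the point. The duty in 6.8.5 applies to use already recognised as rescue, and for TCS that recognition is the uncounted step. Whether PUVA is found should not depend on a dictionary term the SAP does not specify. A record that meets two definitions reported separately needs a rule saying which one applies.

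**Conclusion.** The point holds as a minor one. As written, Appendix 1 can miss phototherapy entered as PUVA, can count one topical ruxolitinib record as both topical and systemic rescue, and leaves the more-than-10-day TCS criterion without a source or a counting rule. The effect is confined to the descriptive summaries in SAP 5.10. Its size is unknown, because the documents do not say how often such records are expected. It also depends on site wording, dictionary coding and the recorded route.

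A reader might infer more: that the primary estimand's statement of no intercurrent events rests on this derivation, and that each missed participant shifts the Week 16 rate by about one point (1/95 = 1.05). The documents do not support that. The statement rests on the protocol's rule that rescue leads to discontinuation, and no SAP text removes or recodes a participant because of the flag. A rescued participant who stayed on treatment would remain in the as-observed analysis whether or not Appendix 1 found the record. Even under an exclusion rule that the SAP does not contain, removing one responder from an assumed 48 of 95 gives 47/94, a move from 50.5% to 50.0%.

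**What to change.** In SAP Appendix 1:

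- Make the phototherapy search case-insensitive and add `PUVA`, `UVA`, `UVB` and `ultraviolet`, in both the reported term and the preferred term. Match the short abbreviations as whole words or leave false hits to the existing manual review, since `uva` also occurs inside drug names such as rosuvastatin. A light-therapy term could be added on the same basis.
- Exclude products already classed as topical from the systemic definition, or remove Transdermal from the systemic route list. The first option keeps any genuinely systemic transdermal product.
- Name the CRF and the diary as the sources for the existing more-than-10-day criterion, and have the sponsor state how days are counted. The Schedule of Activities describes the diary item only as TCS usage, so product and potency would have to come from the CRF record.

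In the protocol, reconcile 6.8.4 with 6.8.5 so that every high-potency TCS product is entered on the CRF from first use. This concerns recording only; the threshold and its consequences for the participant are untouched.

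The cost is a few lines of Appendix 1 and its programming, one recording instruction to sites, and slightly more data entry.
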